5. STUDY ENTRY AND ENROLLMENT AND WITHDRAWAL

5.1 Study Entry

Study entry, as used in this protocol, will be defined as a subject signing informed consent. Study enrollment, as used in this protocol, will be defined as the investigator's confirmation of the subject's eligibility by signing an eligibility checklist. As per University of Miami policy, each study participant, including participants who have screened failed, who signs an informed consent form should be entered into the study database.

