10.5 Statistical Analysis and Power calculation

The average and standard deviation of all relevant variables, including demographic and baseline characteristics, primary and secondary outcomes will be calculated.

IIEF-EF and EHS scores will be analyzed using ANOVA with repeated measures throughout the study, in order to compare the trends of groups A and B.

GAQ, SEP and success rates will be analyzed and compared between the groups according to Fisher's exact test in each of the endpoints. The statistical significance will be set at $P < 0.05$.

Demographic characteristics such as age and ED duration will be compared between groups A and B using student's test. Other demographic characteristics, such as medical background and risk factors will be compared between these groups using Fisher's exact test.

A sample of 80 men with failing scores on the IIEF SEP2 question will be randomized 1:1 into one of two arms (low intensity or high intensity treatment) using a permuted random block algorithm. We hypothesize that following placebo treatment between 0 and 5% of men will pass the SEP2 question and at least 35% of men treated at either intensity level will pass. We have two co-primary

endpoints, the percentage of men passing after low intensity and high intensity relative to placebo, which will be assessed by two independent Fisher’s exact tests. Each of these tests will be conducted with a 0.025 alpha error level to allow for a 0.05 experiment wide type I error rate. Power calculations done in SAS 9.4 suggest that with 40 men randomized into each group we will have at least 85% power to detect the difference between a 5% and 35% response rate. So long as our non-compliance/drop-out rate remains above 10% will will have at least 80% power (see Figure 1).

Computed N per Group			
Index	Nominal Power	Actual Power	N per Group
1	0.80	0.813	37
2	0.85	0.852	40
3	0.90	0.900	45

Figure 1. Sample size needed for 80% 85% and 90% nominal power for a Fisher’s exact test with alpha = 0.025 (using an exact conditional distribution with the Walters normal approximation method).

10.6 Randomization:

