80 patients will be randomized 1:1 to treatment groups with 40 patients each. An online based randomization tool called randomized.org will be used. This will be prepared beforehand, with treatment option printed on the paper and then sealed in an envelope (80 envelopes). Each would have Patients ID number printed out side and randomization information inside. This would be opened after a patient has signed the informed consent and is ready to receive treatment. The PI nor the study coordinator will not have the knowledge of patient’s treatment group beforehand.

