11.2 Confidentiality

The identity of the patients in this study will be treated as confidential. Patients eligible to participate in the study following the pre-treatment visit will be assigned a unique patient code. The results of the study, including any other data, may be published for scientific purposes but will not give the patients' name or include any identifiable references to them.

However, any records or data obtained as a result of the patient participation in this study may be inspected by the sponsor, by any relevant governmental agency, by the Hospital Ethics Committee, or by the persons conducting this study, provided that such inspectors are legally obligated to protect any identifiable information from public disclosure, except where disclosure is otherwise required by law or a court of competent jurisdiction. These records will be kept private in so far as permitted by law.

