11.4 Source Documentation and Investigator Files

The investigator will maintain adequate and accurate records to document the conduct of the study and to ensure that study data can be subsequently verified. These documents will be classified into two separate categories: (1) investigator study file and (2) subject clinical source documents that corroborate data collected on the CRF's. Subject clinical source documents would include hospital/clinic patient records; physician's and nurse's notes; original laboratory, radiology, pathology, and special assessment reports; QOL forms, signed informed consent forms. When the CRF or any form is used as the source document, this will be clearly stated in the investigator study file.

At a minimum, the following be documented in source documents:

- Medical history/physical condition and diagnosis of the subject before involvement in the study sufficient to verify protocol entry criteria.
- Study number, assigned subject number, and verification that written informed consent was obtained (each recorded in dated and signed notes on the day of entry into the study)
- Progress notes for each subject visit.
- Laboratory test results.
- Condition and response of subject upon completion of or early termination from the study.
- Quality of Life Surveys.

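### Section 10.6 ties 80 prepared envelopes to patient IDs, but the protocol conflicts on when the ID is given and when allocation happens, so allocations can go unused; block details are also unstated

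*Combined protocol and SAP*

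**What the plan says.** **Envelopes.** Section 10.6 states the target, "80 patients will be randomized 1:1 to treatment groups with 40 patients each", and prepares 80 sealed envelopes beforehand from an online tool. On labelling: "Each would have Patients ID number printed out side and randomization information inside". On opening: "This would be opened after a patient has signed the informed consent and is ready to receive treatment". As a safeguard it adds "The PI nor the study coordinator will not have the knowledge of" the patient's group in advance.

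**When the ID is given.** Section 11.4 lists the assigned subject number among items "each recorded in dated and signed notes on the day of entry into the study", and 5.1 defines study entry as signing consent. Section 5.1 also requires that "each study participant, including participants who have screened failed, who signs an informed consent form should be entered into the study database". Section 11.2 says something else: "Patients eligible to participate in the study following the pre-treatment visit will be assigned a unique patient code".

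**When and how allocation happens.** Section 7.3 randomises once eligibility has been evaluated, using departmental software, and then describes a 4-week PDE5i washout before the first session. The study calendar (section 17) puts randomisation at Visit 2, ahead of the treatment visits. Section 10.6 uses the online tool and opens the envelope only when the man is ready for treatment.

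**Blocks.** Section 10.5 says patients are randomised "using a permuted random block algorithm". No block size is given, nor whether it varies. Section 10.6 does not mention blocks.

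**The concern.** An envelope that carries a patient ID can serve only the man with that ID. If the ID exists before the envelope is opened, anyone lost in between takes an allocation with him. Losses after consent are to be expected: in 7.2 men sign consent and then complete the IIEF-EF to see whether they qualify, and a 4-week washout follows. No section says what happens to an unused envelope, or to a man whose ID lies beyond the prepared 80. Either the trial stops short of 40 per arm, or extra envelopes are made ad hoc outside the concealed list.

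The timing conflict also affects the analysis set. Section 5.3 applies intention to treat once a man is randomised. A man who drops out during washout is in the analysis under 7.3 and was never randomised under 10.6.

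The second issue is predictability. There is one recruiting clinic (4.1). The schedules differ openly (five daily sessions against three a week for two weeks, 7.4), and no sham or blinding is described. Staff therefore see each allocation once its envelope is opened. If blocks are small and of fixed size, later allocations can be partly inferred. Some exclusions in 6.2 rest on investigator judgement, so such knowledge could influence who is enrolled.

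**Working it through.** **1. The plan's own figure.** Figure 1 in 10.5 uses 5% against 35%, Fisher's exact test, alpha 0.025 and the Walters approximation. With n per group:

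power = Φ{[arcsin√(0.35 − 1/2n) − arcsin√(0.05 + 1/2n)] × √(2n) − 2.241}

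At n = 40: (0.6199 − 0.2527) × 8.944 − 2.241 = 1.043, so power is 0.8515 (stated 0.852). At n = 37 it is 0.813 and at n = 45 it is 0.900, as stated. The figure reproduces. It serves below only as a yardstick, because it compares an active arm with a placebo group that this design does not have.

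**2. Which readings lose envelopes.**
- ID at consent (11.4 with 5.1), envelope opened when ready for treatment (10.6): men who fail screening and men who drop out in washout both leave envelopes unopened.
- ID to eligible men after the pre-treatment visit (11.2), envelope opened when ready for treatment: screen failures cost nothing. Men who drop out in washout still leave envelopes unopened if that visit precedes the washout.
- ID given only at the moment of allocation: nothing is lost, and 80 envelopes give 40 + 40.

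**3. Size of the loss.** The documents give no loss rate, so f is assumed.
- Men randomised from 80 envelopes = 80 × (1 − f): 72, 64 and 56 at f = 10%, 20% and 30%.
- IDs needed to randomise 80 = 80/(1 − f), rounded up: 89, 100 and 115.
- Yardstick power with equal arms of 36, 32 and 28: 0.80, 0.73 and 0.65.

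**4. Arm imbalance.** With m of 80 envelopes opened at random, the number in arm A is hypergeometric (40 of 80). At m = 64 its SD is √(64 × 0.25 × 16/79) = 1.8, so the SD of the arm difference is 3.6 and the 95% range is about ±7. The mean absolute difference is 2.1, 2.8 and 3.2 men at m = 72, 64 and 56. Block sizes from 2 to 80 make almost no difference in simulation. Imbalance costs little: a 44/36 split gives 0.844 on the yardstick against 0.852 for 40/40.

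**5. Predictability.** Assume a fixed block of size 2k whose size staff have inferred, with every earlier allocation seen. The share known for certain is 1/(k + 1). Always guessing the arm with more places left gives a correct share of [k + (4^k / C(2k,k) − 1)/2] / 2k. At k = 2 that is [2 + (16/6 − 1)/2]/4 = 0.708.

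| Block size | Known for certain | Guessed correctly |
|---|---|---|
| 2 | 50% | 75% |
| 4 | 33% | 71% |
| 6 | 25% | 68% |
| 10 | 17% | 65% |
| 80 (one block) | 2.4% | 56% |

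The two problems partly offset each other. If each envelope stays unopened with probability 20%, enumeration gives 40%/70%, 21%/66% and 13%/63% at sizes 2, 4 and 6.

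**The case against.** The best defence reads 11.2 and 10.6 together: only eligible men receive a code, 80 envelopes are meant for 80 randomised men, and each is opened when treatment is about to start. If the code is given at that moment, nothing is lost. Section 11.4 is a generic source-document list and does not say that its subject number is the one on the envelope; 5.1 only puts screen failures in a database. This stands as a possible reading. It does not settle the matter, because 11.2 gives no exact moment and a code issued before washout still leaves a gap. If 7.3 governs instead, men lost in washout are already randomised and 5.3 covers them, but that contradicts 10.6.

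A reader might infer that every screen failure uses up an allocation, or that the balance of the trial would break down. The documents support neither: the loss depends on the reading, 40 and 40 are arm totals rather than blocks, and the expected imbalance is a few men.

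A reader might also infer that staff can foresee allocations. No section says that blocks are small, fixed or known to staff, and one 80-patient list, compatible with 10.6, is close to chance. Section 10.6 also keeps the group from the principal investigator and the coordinator beforehand. That covers the sealed contents, however, not inference from envelopes already opened, and 10.6 does not say who prepares them.

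Finally, most entry criteria are measured values, and the hypotheses in section 2 concern change within groups, which selection between arms does not bias. That limits the impact. But 10.5 also compares groups A and B, and that is the comparison randomisation is there to protect.

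**Conclusion.** The point holds as a conflict in the allocation procedure with a conditional loss. If the ID precedes the opening of the envelope, 80 envelopes randomise fewer than 80 men: 72, 64 or 56 at assumed losses of 10%, 20% or 30%. If the ID is given only at allocation, none is lost. The shortfall matters more than the imbalance: 64 men is 32 per arm, below the 37 per group that Figure 1 gives for 80% power, subject to the placebo caveat.

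Predictability is a separate and also conditional weakness. It is material for small fixed blocks whose size is inferred and slight for one long block. That the trial is open-label is a fair inference from the visible schedules and the absence of any blinding text; the protocol does not use the term.

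This is more than missing detail, because labelling envelopes by ID is a stated rule that fails under plausible readings. It should be changed.

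**What to change.** In 10.6, label the envelopes with a sequential randomisation number separate from the patient ID. Open them strictly in order at the point of randomisation, and log the number, patient ID and date. No man lost earlier then uses up an envelope, and the planned 40 + 40 and the stated 0.852 are unaffected under every reading.

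Have the list generated with randomly varying block sizes by an existing staff member who neither enrols nor treats, and keep the sizes undisclosed, as they are now.

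Reconcile 11.2 with 11.4 and 5.1 on when the ID is given. Reconcile 7.3 and the calendar with 10.6 on the randomisation tool and on whether randomisation precedes or follows washout, so that the intention-to-treat rule in 5.3 has a clear starting point.

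The cost is re-labelling and a new list before the first patient, with no added staff or visits. The one downside is a possible slight imbalance if the last varying block is incomplete.

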11. INVESTIGATORS RESPONSIBILITIES

11.1 Investigator Responsibility/Performance

The investigator (or a person designated by the investigator) should inform the patient of all pertinent aspects of the study, including the written information.

The investigator should provide the patient ample time and opportunity to inquire about details of the study and to decide whether or not to participate in the study. All questions about the study should be answered to the satisfaction of the patient. Neither the investigator, nor the study staff, should coerce or unduly influence a patient to participate or to continue to participate in a study.

11.2 Confidentiality

The identity of the patients in this study will be treated as confidential. Patients eligible to participate in the study following the pre-treatment visit will be assigned a unique patient code. The results of the study, including any other data, may be published for scientific purposes but will not give the patients' name or include any identifiable references to them.

However, any records or data obtained as a result of the patient participation in this study may be inspected by the sponsor, by any relevant governmental agency, by the Hospital Ethics Committee, or by the persons conducting this study, provided that such inspectors are legally obligated to protect any identifiable information from public disclosure, except where disclosure is otherwise required by law or a court of competent jurisdiction. These records will be kept private in so far as permitted by law.

11.3 Informed Consent and Permission to Use Protected Health Information

It is the responsibility of the investigator to obtain written informed consent from each subject participating in this study after adequate explanation, in lay language, of the methods, objectives, anticipated benefits, and potential hazards of the study. The investigator must also explain that the subject is completely free to refuse to enter the study or to discontinue participation at any time (for any reason) and receive alternative conventional therapy as indicated. Prior to study participation, each subject will sign an IRB approved informed consent form and receive a copy of same (and information leaflet, if appropriate).

The investigator or designee **must** explain to the subject before enrollment into the study that for evaluation of study results, the subject's protected health information

obtained during the study may be shared with the study sponsor, regulatory agencies, and the IRB. It is the investigator's (or designee's) responsibility to obtain permission to use protected health information per HIPAA from each subject, or if appropriate, the subjects' parent or legal guardian.

11.4 Source Documentation and Investigator Files

The investigator will maintain adequate and accurate records to document the conduct of the study and to ensure that study data can be subsequently verified. These documents will be classified into two separate categories: (1) investigator study file and (2) subject clinical source documents that corroborate data collected on the CRF's. Subject clinical source documents would include hospital/clinic patient records; physician's and nurse's notes; original laboratory, radiology, pathology, and special assessment reports; QOL forms, signed informed consent forms. When the CRF or any form is used as the source document, this will be clearly stated in the investigator study file.

At a minimum, the following be documented in source documents:

- Medical history/physical condition and diagnosis of the subject before involvement in the study sufficient to verify protocol entry criteria.
- Study number, assigned subject number, and verification that written informed consent was obtained (each recorded in dated and signed notes on the day of entry into the study)
- Progress notes for each subject visit.
- Laboratory test results.
- Condition and response of subject upon completion of or early termination from the study.
- Quality of Life Surveys.

11.5 Recording and Processing of Data

Data for this study will be entered into electronic CRFs in research database (a web-based clinical research management application). A CRF is required for every patient who received any study intervention. The investigator will ensure that the CRF's are accurate, complete, legible and timely. Separate source records are required to support all CRF entries. All corrections to study data will be made by drawing a single line through the information to be corrected without obscuring

it. All corrections will be initialed, dated and explained, if necessary. **Do not use “white-out” or obscuring correction tape.**

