5.3 Cancellation Guidelines

The following are reasons for withdrawal of subjects from the study:

- A subject does not meet the eligibility criteria; (the subject will be considered a screen failure).
- A subject withdraws consent,
- A subject die's during protocol participation from causes other than the study treatment (not due to adverse events) or
- A study investigator decides the subject should be withdrawn from the study (e.g. subject non-compliance)

Regardless of reason for withdrawal, once a patient has been randomized to an arm, an intention to treat analysis will be performed.

All subjects who either screen fails, is withdrawn from the study or has completed all visits should be de-enrolled from the research database within 48 hours.

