7.3 Pre-Treatment Procedures and Evaluations

Upon evaluating the inclusion/exclusion criteria, patients will be recruited to the study and randomized into one of the two groups in a 1:1 ratio (randomization will be performed by a computer software maintained by the Department of Urology). Patients randomized to the treatment groups will be instructed to stop any use of PDE5i for 4 weeks prior to first treatment session and refrain from using any other ED therapy option during the study. They will be instructed to undergo a PDE5i washout period of 4 weeks prior to treatment and to avoid using PDE5i or any other ED treatment during the entire study duration (shockwave treatment and follow-ups). After the washout period and before the first treatment session, patients will answer the IIEF-EF, SEP and EHS questionnaires for baseline evaluation.

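### The intention-to-treat analysis promised in 5.3 is not supported by the data-collection rules: baseline and outcome data for men who leave early are not secured

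*Combined protocol and SAP*

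**What the plan says.** **Analysis rule.** Section 5.3: "Regardless of reason for withdrawal, once a patient has been randomized to an arm, an intention to treat analysis will be performed".

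**Withdrawal.** One of the grounds listed in 5.3 is "A study investigator decides the subject should be withdrawn from the study (e.g. subject non-compliance". The section ends by saying that a man who fails screening, "is withdrawn from the study or has completed all visits should be de-enrolled from the research database within 48 hours".

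**Data capture.** Section 11.5: "A CRF is required for every patient who received any study intervention". Section 5.1 sets a wider rule for the database: "each study participant, including participants who have screened failed, who signs an informed consent form should be entered into the study database".

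**Timing of randomisation.** In 7.3, once eligibility has been checked, "patients will be recruited to the study and randomized into one of the two groups in a 1:1 ratio", and then "They will be instructed to undergo a PDE5i washout period of 4 weeks prior to treatment". The baseline IIEF-EF, SEP and EHS come after that washout. Section 10.6 says of the sealed allocation envelope: "This would be opened after a patient has signed the informed consent and is ready to receive treatment".

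**Follow-up and analysis.** Section 7.5 schedules visits at months 1, 3 and 6. Section 10.5 names a repeated-measures ANOVA for IIEF-EF and EHS, and Fisher's exact test for SEP and GAQ. It defines no analysis set and gives no method for missing data.

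**The concern.** An intention-to-treat analysis needs two things: a list of everyone randomised, by arm, and baseline and outcome data for the men on it. The protocol provides the first but does not secure the second.

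The only randomised comparison is Group A (five sessions in one week) against Group B (three sessions a week for two weeks, so six). The burden of attendance differs, so missed sessions and withdrawals could differ too. Non-compliance is not defined, the decision is the investigator's, and no masking is described once the envelope has been opened. If outcomes go missing for reasons linked to the schedule, the men left in each arm are no longer comparable, and randomisation no longer protects the A versus B contrast.

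**Working it through.** The plan gives no figure for this point, so the check is mainly a comparison of sections.

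1. **Can the randomised men be listed?** Yes. Section 5.1 puts every consenting man in the database. Section 10.6 prepares 80 envelopes, each with a patient ID outside and the allocation inside.

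2. **Does the CRF rule cover the same men?** Not necessarily. The intention-to-treat population is defined by randomisation, but the mandatory CRF is defined by receipt of an intervention. No sentence requires a CRF for a man who was randomised and not treated.

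3. **How many such men could there be?** That depends on timing.
   - Under 7.3, randomisation precedes a four-week washout. A man who leaves during it has been randomised, has no required CRF, and lacks the post-washout baseline. He would have only his screening answers.
   - Under 10.6, the envelope is opened when he is about to be treated. Few randomised men would then go untreated.
   - The study calendar places randomisation at the pre-treatment visit, which does not say on which side of the washout it falls.

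4. **What happens after treatment starts?** Under either timing, 5.3 allows withdrawal from the study, not only from the sessions. No section asks a withdrawn man to return at months 1, 3 and 6. Section 11.4 requires a source note of his condition and response at early termination, but that does not replace the scheduled questionnaires.

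5. **Would the analysis cope?** Section 10.5 does not say. A classical repeated-measures ANOVA normally uses only men with all visits complete.

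6. **Scale, under an assumption.** The only loss rate the plan names is 10%, in the power paragraph of 10.5, and it is not a forecast. Assume that 5% to 10% of 40 men per arm have no outcome: 0.05 × 40 = 2 and 0.10 × 40 = 4. Take a yes/no outcome such as SEP2, with x successes observed and m men missing in an arm. The success rate over all 40 lies between x/40 and (x + m)/40. With m missing in each arm, the A minus B difference is known only within a band of width 2m/40:
   - m = 2: 4/40 = 10 percentage points
   - m = 4: 8/40 = 20 percentage points

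   These are the widest limits that the missing men allow. They do not estimate the bias.

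7. **The power table in 10.5.** It reproduces. The Walters approximation is power = Φ(h√(n/2) − z), where h = 2[arcsin√(0.35 − 1/(2n)) − arcsin√(0.05 + 1/(2n))] and z is the two-sided 0.025 quantile. It gives 0.813, 0.852 and 0.900 for n = 37, 40 and 45, as printed. It compares an active arm with placebo, so it does not measure the A versus B bias discussed here.

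**The case against.** The strongest reply is that the protocol already commits to intention to treat, enters every consenting man in its database, records allocation by ID, and asks for source notes at early termination. On that view the analysis set exists and the rest is ordinary missing data. Much of this stands, and it rules out several stronger conclusions that a reader might draw.

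- *That the intention-to-treat set cannot be built.* Sections 5.1 and 10.6 allow it to be listed by arm. What is unsecured is the data.
- *That untreated men may not have a CRF.* Section 11.5 sets a minimum and does not contain the word *only*. It also says, without limit to treated men, that study data go into electronic CRFs. But a site that meets the minimum exactly could still have no CRF for a randomised man.
- *That de-enrolment deletes data.* The same 48-hour step applies to men who complete every visit, so it reads as a change of status. The text should say so.
- *That the analysis becomes one of treated, compliant men.* Section 5.3 states the opposite intention, and missing outcomes do not by themselves turn a declared intention-to-treat analysis into a per-protocol one.
- *That the harm can be stated as lost power.* The calculation in 10.5 compares each arm with a placebo group that this two-active-arm trial does not have. Any result would also depend on an assumed loss rate and on a rule for counting missing men that the protocol does not contain.

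The reply also fairly notes that the washout gap largely disappears if 10.6 governs. It does not answer the lack of follow-up after withdrawal, which applies under either timing, or the absence of a missing-data method.

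**Conclusion.** The point holds as a mismatch between the promised analysis and the rules for collecting its data. Following the plan as written can lose baseline data (under 7.3) and outcome data (under either timing) for men already randomised, and 10.5 does not say how the losses would be handled.

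Bias in A versus B arises only if withdrawal, or the reasons for it, differ between the schedules. The documents neither show nor exclude that, so its size cannot be derived from them. The 10 to 20 point band rests on the assumed 5% to 10% loss in each arm and shows only how much a few missing men could leave open with 40 per arm. The plan should be corrected on this point, but the defect does not by itself invalidate the trial.

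**What to change.** - **11.5:** require a CRF for every randomised patient.
- **5.3:** separate stopping study sessions from leaving the study. Unless consent is withdrawn, men who stop or do not comply still complete the month 1, 3 and 6 questionnaires. De-enrol only after month 6 or withdrawal of consent, and state that de-enrolment does not remove data already collected.
- **10.5:** define the intention-to-treat set as all randomised men, analysed as randomised. For IIEF-EF and EHS, use an analysis that keeps men with incomplete visits, for example a mixed model for repeated measures. State in advance how missing SEP and GAQ answers enter the Fisher tests. A mixed model cannot supply outcomes for men who have none, so continued follow-up matters more than the choice of model.
- **7.3 and 10.6:** reconcile the time of randomisation, so that it is clear which men are randomised before treatment and whether their baseline comes before or after allocation.

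The cost is a few sentences of text, a few more CRFs, and questionnaire visits that are already in the calendar.
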